## 2.0 Study Protocol

### 2.1 Protocol ID and Title

Protocol: BREC-TSMU#2-2023/103.

The research implementation of the clinical model for evaluation of the CYP2C19 allele genotype-guided clopidogrel treatment.

### 2.2 Protocol Version and the Date

Version: #2-2023/103

The revision of protocol version #2023/1.0, which was primarily submitted to the Biomedical Research Ethics Committee of Tbilisi State Medical University for review by May 24, 2023, was revised with additional explanations and clarifications by the IRB conditions and notes, and finally approved on June 7, 2023.

The definitions and clarifications presented in this protocol version do not change the essence of study participants' selection criteria and do not reflect the study design, methodology, study procedures, the measures for observing effects and safety, or the expected results, either qualitatively or quantitatively.

The revisions and updated definitions presented only increase the pool of patients from whom study participants should be selected in real clinical practice, and facilitate and support researchers/investigators in conducting subject selection, study procedures, and monitoring efficacy and safety in a targeted manner.

### 2.3 Study Design

[figure not shown]
#### 2.3.1 General Design

Randomized Parallel Group Controlled Trial for Evaluating CYP2C19 Allele Genotype-guided Clopidogrel Treatment Outcomes in Real-world Practice After the ePCI.

### 2.3.2 Structural Design

Study participants will be recruited from 4 or more clinical centers. Based on informed consent, these centers will be selected and employed to provide study-specific activities under the condition that they provide CAD-specific diagnostic, treatment, and prevention services as recommended by current guidelines in their real-world clinical practice. They must provide GCP-compliant care based on current quality standards, patient best interests, and safety.

A logical model of study.

A population of patients who require antiplatelet therapy with a P2Y12 inhibitor following ePCI in CAD CCS cases within the framework of the recommendations for the use of DAPT (ESC, ACC/AHA) will be pre-assigned from the centers' real-world practice. Eligible patients will be considered for participation in the study after formal informed consent for inclusion in the specific clinical study measures.

Screening measures will be implemented for these patients to establish study inclusion and exclusion criteria. In conditions of the existence of inclusion criteria and absence of exclusion criteria, study participants will be randomized to the study or control arm by control-to-experiment allocation rate 1:2.

Study participants randomly allocated to the experimental arm will undergo laboratory blood testing for CYP2C19 \*2, \*3 genotyping using the RT-PCR-based allele discrimination method. According to the results of genotyping, the study participants will be assigned to two experimental treatment arms:

1st experimental arm will consist of the study participants with the active metabolizing phenotype of CYP2C19 (a normal function CYP2C19 \*2, \*3 allele (NFA) genotype), who will receive clopidogrel-based antiplatelet treatment;

2nd experimental arm will consist of study participants with the passive metabolizing phenotype of CYP2C19 (a loss-of-function CYP2C19 \*2, \*3 allele (LOF) genotype, heterozygous or homozygous), who will receive alternative antiplatelet treatment of clopidogrel.

Study participants allocated to the control arm – 3rd arm of active comparators will not undergo laboratory blood testing for CYP2C19 \*2, \*3 genotyping, will be considered as study participants with unspecified metabolizing phenotype of CYP2C19 and receive the P2Y12 inhibitor clopidogrel-based antiplatelet treatment according to current clinical practice recommendations, without genotyping for CYP2C19 \*2, \*3 alleles as by real-world practice.

All study participants assigned to the study arms will undergo baseline and ongoing clinical follow-up to assess clinical endpoints as study clinical outcomes.

All clinical cases will be followed up with the primary, secondary and other prespecified clinical endpoints of the study and routine clinical indicators of safety at 3, 6, and 12 months. Non-clinical study outcomes will be assessed and compiled with other results of the outcome measures.

Study monitoring and evaluation procedures will be implemented alongside the study activities to assess safety and efficacy, and outputs.

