The current paradigm for clopidogrel use faces a dilemma. Existing practice guidelines (ESCARDIO, 2017 and ACC/AHA, 2016) provide recommendations for the use of clopidogrel or other P2Y12 inhibitor treatment without CYP2C19 genotyping. A larger evidence base supporting the efficacy of the pharmacogenetic approach is required to guide treatment recommendations based on CYP2C19 genotyping, including genome-wide associations between CYP2C19 genotype variability and MACCE of recurrent ASCVD on clopidogrel treatment [8, 10]. On the other hand, the 2019 Global Consensus Report of the industry associations presented the possibility of tailoring P2Y12 inhibitor treatment based on CYP2C19 genotype and general recommendations for the selective use of CYP2C19 genetic testing [10]. The FDA's so-called "Clopidogrel" "Black box warnings" [18], EMA precautionary statements, CPIC and DPWG scientific reports [19-21], as well as the evidence base from new pragmatic and prospective studies [9-16], support the approach of CYP2C19 allele-specific P2Y12 inhibitor treatment and determine its efficacy. Approximately 30% of the European population and 60% of Asians carry CYP2C19 non-functional alleles [21], which are associated with resistance to clopidogrel treatment and a significantly increased risk of MACCE [21-24].

At this stage, the directions of scientific development can be determined by the following research questions: Can CYP2C19 allele genotypes be routinely used for P2Y12 inhibitor treatment? The answer to the main question will make a significant contribution to resolving this issue: Are CYP2C19 genetic variations associated with clinical outcomes of clopidogrel treatment independent of interactions with other known factors?

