## 2.4.2 Expected Number of Study Participants

Patients with stable CAD who have undergone ePCI coronary artery stenting without clinically significant procedural complications, require conventional antiplatelet therapy with a P2Y12 inhibitor, meet inclusion criteria, do not present exclusion criteria, and provide informed consent for participation will be selected and randomized for the study.

The sample size of 240 study participants is determined for inclusion in the study. Calculations were made using two instruments that provided two approximate sample sizes. The median of these values (considering that the greater level of significance of the odds ratio and the relative absolute risk values could be achieved with the larger sample size) was taken as the sample size.

(1) Calculate the sample size for scientific studies using a standard numerator based on the proportion of the population that is likely to have the demographic characteristics of the study sample and the size (number) of the population with the clinical characteristics expected for the study, with a 95% confidence level and a  $\pm 5\%$  confidence interval for the results of the statistical calculations.

(2) Sample size calculation for a randomized, parallel case-control study with a two-sided statistical significance level, at a confidence interval of  $\alpha = 0.05$ , at statistical power of  $(1-\beta) = 0.8$ , at case/control ratio of 2, at probability of occurrence of an event in the experimental arm of  $p_0$  – up to 0.4, and at probability of occurrence of an event in the control arm of  $p_1$  – up to 0.6.

Study participants will be randomly assigned to two parallel groups, control and experimental, with a 1:2 allocation ratio and selected 3 study arms for participants by CYP2C19 genotyping results:

1st arm – experimental: "Normal Metabolizers of Clopidogrel", 110 study participants diagnosed with chronic coronary artery disease who had undergone elective PCI, tested with CYP2C19 genotyping and identified as NFA \*2, \*3 carriers, who undergo CYP2C19 Genotype-Guided Clopidogrel Treatment - Clopidogrel as a component of preventive antiplatelet treatment such as double antiplatelet treatment (DAPT), or an antiplatelet drug (clopidogrel) combined with the non-vitamin K antagonist oral anticoagulants (NOAC), incl. triple antiplatelet treatment (Aspirin, Clopidogrel and a NOAC), or antiplatelet monotherapy (Clopidogrel).

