## **(2) Sample size calculation for a randomized, parallel, case-control study.**

This tool for calculating the study sample size in a selected population will demonstrate reliable statistical relationships and estimate the effects of factors on the development of disease outcomes. With a two-sided statistical relationship, a confidence interval of  $-\alpha - 0.05$ , a power of  $(1-\beta) - 0.8$ , a case/control ratio of  $-2$ , a probability of developing an event in the case group -  $p_0$  - up to 0.4, and a probability of developing an event in the control group -  $p_1$  - up to 0.6, the calculated sample size is determined as a minimum 221 patients.

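### Sample-size calculation (2) assumes 0.6 v 0.4 between the randomised groups although about 69% of the guided group receives the controls' drug, so it implies a fall of about 64 points in LOF carriers

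*Combined protocol and SAP*

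**What the plan says.** Participants are randomised 1:2 to control or guided treatment (2.3.2). Three statements fix the drug contrast:

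- Controls are not genotyped and "receive the P2Y12 inhibitor clopidogrel-based antiplatelet treatment according to current clinical practice recommendations".
- Guided participants with normal-function alleles form arm 1, "who will receive clopidogrel-based antiplatelet treatment".
- Guided LOF carriers form arm 2 and receive an alternative to clopidogrel.

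Planned numbers (2.4.2) are 110 in arm 1, about 50 in arm 2 and 80 controls. The arm 1/arm 2 split is extrapolated from European data. Section 1.3 states "Approximately 30% of the European population and 60% of Asians carry CYP2C19 non-functional alleles", and 2.4.2 says the prevalence in Georgia has not been studied.

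N = 240 combines two results in 2.6.2. Calculation (1) is a survey-type precision calculation giving 251. Calculation (2) uses two-sided alpha 0.05, power 0.8, a ratio of 2, and event probabilities of up to 0.4 (experimental) and up to 0.6 (control). Under it, "the calculated sample size is determined as a minimum 221 patients". It names no endpoint.

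The listed comparisons are arm 1 v controls (Control 1), arm 2 v controls (Control 2) and arm 1 v arm 2 (Control 3). Appendix 3 adds arms 1 and 2 aggregated v controls.

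**The concern.** Randomisation compares two strategies, but the strategies prescribe a different P2Y12 inhibitor only for LOF carriers. Any drug-driven difference between the randomised groups is therefore the LOF-carrier effect multiplied by the LOF share. Calculation (2) enters a 20-point difference between the groups and nowhere asks what this requires of the minority whose drug changes. The dilution applies to any endpoint and any event rate, so correcting the rates alone would not remove it.

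At stake is the claim of 80% power. If it rests on an effect the design can hardly produce, a null result would be read as evidence against genotype guidance when the trial could not have detected a realistic benefit. Emphasis might then move to Control 2, which sets an all-LOF arm against controls of mixed genotype and does not isolate the drug effect in LOF carriers.

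**Working it through.** **Inputs.** Guided 160 = 110 + 50 and controls 80 (2.4.2; 2.5.9 also gives 160 to be genotyped). LOF share f = 50/160 = 0.3125. p(control) = 0.6, p(guided) = 0.4, ratio 2, two-sided alpha 0.05, power 0.8 (2.4.2 and 2.6.2). MACCE probability 1–10% (3.2.1).

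**1. The plan's figure reproduces.** Weighted mean risk = (0.6 + 2 × 0.4)/3 = 0.4667.
Controls = (1.960 + 0.842)² × 0.4667 × 0.5333 × 1.5 / 0.20² = 73.26, so 74 controls and 2 × 73.26 = 146.5, so 147 guided. The total is 221, as stated. At 80/160 the same inputs give 84% power.

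**2. Its role in N.** (221 + 251)/2 = 236, taken upward to 240. The 251 contains no treatment effect: the usual finite-population formula with p = 0.24, margin 5% and population 2056 gives 247, close to it.

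**3. Implied effect in LOF carriers.** With no effect in normal-allele carriers, overall difference = f × LOF difference, so LOF difference = 0.20/f.

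| LOF share | Required LOF reduction |
|---|---|
| 25% | 80 points |
| 30% | 67 points |
| 31.25% (planned) | 64 points |
| 35% | 57 points |
| 40% | 50 points |

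**4. Can 64 points occur?** With an overall control risk of 0.60, normal-allele risk = (0.60 − 0.3125 × LOF risk)/0.6875.

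- Lower end: LOF risk 0.64 on clopidogrel falling to 0, with normal-allele risk 0.58.
- Upper end: LOF risk 1.00 falling to 0.36, with normal-allele risk 0.42.
- If LOF controls have the same 0.60 risk as all controls, preventing every LOF event gives 0.3125 × 0.60 = 18.75 points, short of 20. Under that condition 20 points needs a LOF share of at least 0.20/0.60 = 33%.

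**5. Against the protocol's own event probability.** A control risk of at most 10% cannot fall by 20 points, whatever the genotype mix. With equal control risk by genotype and every LOF event prevented, 10% v 6.875% has about 15% power at 80/160, and 1% v 0.6875% about 5% (normal approximation, rough at so few events).

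**6. Illustration: 20 points confined to LOF carriers.** Overall difference = 0.3125 × 0.20 = 0.0625, for example 0.60 v 0.5375. Pooled risk = (80 × 0.60 + 160 × 0.5375)/240 = 0.5583, null SE 0.0680, alternative SE 0.0675. Then z = (0.0625 − 1.96 × 0.0680)/0.0675 = −1.05, so power is about 15%. Placing the lower risk at 0.40 (0.4625 v 0.40) also gives 15%.

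**7. What Control 2 estimates.** Assumed risks: 8% normal-allele, 14% LOF on clopidogrel, 8% LOF on the alternative.

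- Control risk = 0.6875 × 8% + 0.3125 × 14% = 9.875%.
- Control 2 = 8 − 9.875 = −1.9 points, against a true LOF effect of −6.0. Control 1 also gives −1.9, although arm 1's drug is unchanged.
- Aggregated guided risk = 8%. Rescaled: (9.875 − 8)/0.3125 = 6.0 points. Its SE, ignoring uncertainty in f, is √(0.09875 × 0.90125/80 + 0.08 × 0.92/160)/0.3125 = 0.0397/0.3125 = 12.7 points.

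**The case against.** The strongest reply is that 0.6 and 0.4 are entered as group-level probabilities, so any dilution is already inside them, and that the outcome hypothesis concerns guided against conventional selection. The second half stands. The aggregated contrast in Appendix 3 is a valid randomised estimate of the strategy effect and answers that hypothesis. The first half does not rescue the input: a group-level 20 points is legitimate to assume, but it still needs the LOF effect in step 3, which the plan never states or defends.

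Zero effect in normal-allele carriers is an assumption. Section 2.5.4 discloses genotype to participants and the care team, and regimens within each arm are open, so a non-drug effect is possible.

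Four stronger readings are tempting but not supported:

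- **All of N rests on the 20 points.** It is one of two bases; the 251 has no effect in it.
- **The trial has 15% power.** No document places 0.6 v 0.4 within LOF carriers. That figure is an illustration.
- **Arm 2 has no planned effect measure, so excess bleeding is hidden.** Section 2.6.3 plans effect measures with 95% CIs from both experimental arms' rates and the comparator's. Appendix 3 omits arm 2 v control effect rows but lists arm 2 rates for major and minor bleeding beside the control rates.
- **Control 2 is always wrong.** It equals the LOF drug effect when genotype does not affect the outcome on clopidogrel. That may hold for some outcomes, but for ischaemic events it contradicts the trial's premise.

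The rescaled LOF estimate is also no clear improvement. In the example its SE is 12.7 points, whereas Control 2 has bias 4.1 and SE 5.1, a root mean square error of about 6.5. It therefore belongs in the plan only as an option.

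**Conclusion.** The point holds as a sample-size and labelling issue. Calculation (2) makes no allowance for 110 of 160 guided participants receiving the controls' P2Y12 inhibitor. Assuming no effect of guidance in normal-allele carriers, its 20-point difference implies a 64-point reduction in LOF carriers at the planned share, or 50 to 80 points over shares of 40% to 25%. It is unattainable at the planned share if LOF controls have the general 0.60 risk (maximum 18.75 points), and at any share if the event is MACCE at the protocol's own 1–10%. The 80% power is therefore unsupported. The actual power cannot be stated until the endpoint, event rate and LOF effect are given.

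A reader might infer that the trial cannot validly estimate anything about guidance. It can: aggregated guided v control is valid for the strategy. What no planned contrast estimates directly, without a further assumption, is the drug effect in LOF carriers, because controls are not genotyped.

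**What to change.** 1. **Section 2.6.2 (and the matching text in the synopsis and 2.4.2).** Name the endpoint. State the assumed effect in LOF carriers at an event rate consistent with 3.2.1. Multiply it by the LOF share over a stated range, for example 25% to 40%. Replace the 80% claim with the resulting power for aggregated guided v control at 160/80.
2. **Sections 2.4.2 and 2.6.3 and Appendix 3.** Make the aggregated randomised contrast the main comparison. Label Control 2 descriptive, noting that it equals the LOF drug effect only if genotype does not affect outcome on clopidogrel.
3. **Optional, exploratory.** Report (control rate − aggregated guided rate)/observed LOF share with a 95% CI. State that it is very imprecise (SE about 13 points at the assumed 8/14/8% risks) and assumes no effect of guidance in normal-allele carriers.

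Items 1 and 2 cost wording and a short recalculation; item 3 adds a few rows. None needs new data. The real cost is candour: at event rates in the protocol's own range the restated power will be low, and the trial may have to be presented as estimating the strategy effect with wide intervals.

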## 2.4 Study Participant Selection

### 2.4.1 General Characteristics of Study Participants

Study participants are patients requiring treatment with clopidogrel or an alternative P2Y12 inhibitor following ePCI as a major cardiovascular clinical event for CAD.

Study participants will be selected based on a clinical model defined by stable CAD confirmed by ePCI. They have undergone coronary stenting within the past 12 weeks to reduce their risk, and despite this reduction, they are still at risk of developing recurrent MACCEs. To reduce the risk of subsequent MACCE, the patient with these clinical characteristics requires antiplatelet therapy with clopidogrel after coronary stenting. Carriers of CYP2C19 \*2, \*3 LOF alleles, as patients at complement risk due to expected resistance to clopidogrel treatment, will be given antiplatelet therapy with an alternative P2Y12 inhibitor to clopidogrel for prevention.

In contrast to primary PCI for the management of CAD STE/NSTE-ACS or coronary artery bypass grafting, patients selected with the study clinical model have a relatively lower risk of developing recurrent MACCEs. By equalizing or excluding complementary cardiovascular risky conditions, and co-morbidities, which will be achieved by using study participants' inclusion and exclusion criteria, precise antiplatelet therapy using P2Y12 inhibitors and ensuring adherence to treatment at baseline the probability of recurrent MACCE cases will be equal for the experimental and control arm of study participants. Thus, it will be possible to follow-up and evaluate the clinical outcomes of CYP2C19 genotype-guided as well as conventional treatment with P2Y12 inhibitors (clopidogrel or alternative) which is the aim of the study.

## 2.4.2 Expected Number of Study Participants

Patients with stable CAD who have undergone ePCI coronary artery stenting without clinically significant procedural complications, require conventional antiplatelet therapy with a P2Y12 inhibitor, meet inclusion criteria, do not present exclusion criteria, and provide informed consent for participation will be selected and randomized for the study.

The sample size of 240 study participants is determined for inclusion in the study. Calculations were made using two instruments that provided two approximate sample sizes. The median of these values (considering that the greater level of significance of the odds ratio and the relative absolute risk values could be achieved with the larger sample size) was taken as the sample size.

(1) Calculate the sample size for scientific studies using a standard numerator based on the proportion of the population that is likely to have the demographic characteristics of the study sample and the size (number) of the population with the clinical characteristics expected for the study, with a 95% confidence level and a  $\pm 5\%$  confidence interval for the results of the statistical calculations.

(2) Sample size calculation for a randomized, parallel case-control study with a two-sided statistical significance level, at a confidence interval of  $\alpha = 0.05$ , at statistical power of  $(1-\beta) = 0.8$ , at case/control ratio of 2, at probability of occurrence of an event in the experimental arm of  $p_0$  – up to 0.4, and at probability of occurrence of an event in the control arm of  $p_1$  – up to 0.6.

Study participants will be randomly assigned to two parallel groups, control and experimental, with a 1:2 allocation ratio and selected 3 study arms for participants by CYP2C19 genotyping results:

1st arm – experimental: "Normal Metabolizers of Clopidogrel", 110 study participants diagnosed with chronic coronary artery disease who had undergone elective PCI, tested with CYP2C19 genotyping and identified as NFA \*2, \*3 carriers, who undergo CYP2C19 Genotype-Guided Clopidogrel Treatment - Clopidogrel as a component of preventive antiplatelet treatment such as double antiplatelet treatment (DAPT), or an antiplatelet drug (clopidogrel) combined with the non-vitamin K antagonist oral anticoagulants (NOAC), incl. triple antiplatelet treatment (Aspirin, Clopidogrel and a NOAC), or antiplatelet monotherapy (Clopidogrel).

2nd arm - experimental: "Passive Metabolizers of Clopidogrel", approximately† 50 study participants diagnosed with chronic coronary artery disease who had undergone elective PCI, tested with CYP2C19 genotyping, identified as LOF \*2, \*3 allele carriers, who undergo CYP2C19 Genotype Guided Antiplatelet Treatment Alternative to Clopidogrel - an antiplatelet drug alternative to clopidogrel in conventional dosing regimen, as a component of preventive antiplatelet treatment, such as double antiplatelet treatment (DAPT) with ticagrelor or prasugrel, or prasugrel combined with the nonvitamin K antagonist oral anticoagulants (NOAC), or antiplatelet monotherapy (ticagrelor, or prasugrel).

3rd arm - active comparator: "Unspecified Metabolizers of Clopidogrel", 80 participants diagnosed with chronic coronary artery disease who had undergone elective PCI were allocated to the arm, without CYP2C19 genotyping through simple randomization, and having an unspecified metabolism phenotype, who were assigned to the conventional clopidogrel treatment - clopidogrel as a component of preventive antiplatelet treatment, such as double antiplatelet treatment (DAPT), or clopidogrel combined with the non-vitamin K antagonist oral anticoagulants (NOAC), incl. triple antiplatelet treatment (Aspirin, Clopidogrel and a NOAC), or antiplatelet monotherapy (Clopidogrel).

† The prevalence of carriers of CYP2C19 \*2, \*3 non-functional alleles in the Georgian population has not been studied and is unknown. To estimate the number of patients in subgroup II arm 1 and arm 2, we used the extrapolation of known data from a European population study [12].

2 study arms could be used as control for analyzing and comparing study outcome measures: 3rd study arm participants create the active comparators' group for 1st and 2nd arm, and besides, 2nd study arm participants - as the comparators for 1st arm:

Control 1: "Normal Metabolizers of Clopidogrel" - 110 study participants vs "Unspecified Metabolizers of Clopidogrel" - 80 participants;

Control 2: "Passive Metabolizers of Clopidogrel" - approximately 50 participants vs "Unspecified Metabolizers of Clopidogrel" - 80 participants;

Control 3: "Normal Metabolizers of Clopidogrel" - 110 study participants vs "Passive Metabolizers of Clopidogrel" - approximately 50 participants.

It is reasonable to assume that 75% of the selected study subjects will complete the study activities in full by 12 months of follow-up after enrollment. A portion of the 25% of patients are expected to drop out of the study for various reasons. Withdrawal by study participants, non-compliance with treatment, loss to follow-up and physician decisions are expected as the possible reasons for the study's non-completion.

Some of the dropped-out study participants will undergo appropriate clinical assessments at the interim follow-up periods (before 3, 6, or 12 months) or at the time of early withdrawal from the study and are therefore also considered a source of study data.

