Sample size	
The sample size for the study was determined to be 240 patients.
 
Calculations were made using two instruments that provided two approximate sample sizes. The median of these values (considering that the better the odds ratio could be achieved from the larger the sample size) was taken as the sample size.
 
(1) Calculate the sample size for scientific studies using a standard numerator based on the proportion of the population that is likely to have the demographic characteristics of the study sample and the size (number) of the population with the clinical characteristics expected for the study, with a 95% confidence level and a <math>\pm 5\%</math> confidence interval for the results of the statistical calculations.

	
(2) Sample size calculation for a randomized, parallel case-control study with a two-sided statistical significance level, at a confidence interval of <math>\alpha = 0.05</math>, at statistical power of <math>(1-\beta) = 0.8</math>, at case/control ratio of 2, at probability of occurrence of an event in the experimental arm of <math>p_0</math> – up to 0.4, and at probability of occurrence of an event in the control arm of <math>p_1</math> – up to 0.6.

Data processing	
The study data will be processed in stages when:
 
I - More than 50% of patients are enrolled in the study;
 
II - The study group is fully formed, and by this time, more than 50% of patients have completed the 3-month observation period, and some patients have completed the 6-month observation period.
 
III - all patients included in the study have completed the 6 months, and some have completed the 12 months;
 
IV - All patients included in the study have completed the 12-month observation period.
 
The following will be carried out during the follow-up periods:
 

— Observation of MACCEs and collection of information about them;

— Monitoring and evaluation of the project;

— Observation and analysis of study activities, procedures, non-clinical outcomes and safety data.

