## **2.5.9 Processing of Biological Study Material**

As part of the study, blood samples from study participants will be processed for CYP2C19 genotyping. In addition, during the observation period, study subjects may undergo routine clinical tests by processing blood and urine samples.

Laboratory testing for CYP2C19 genotyping should be performed on at least 160 patients randomized to the study treatment arm for clopidogrel or an alternative P2Y12 inhibitor treatment intervention and for allocation to the appropriate study arm. Blood samples will be processed for this analysis only once during the study period.

The sample laboratory examination for CYP2C19 \*2, \*3 allele genotyping will be carried out in the Ltd "Vistamedi" diagnostic laboratory.

The analysis requires a 3 ml venous blood sample, obtained by simple venipuncture manipulation. The blood sample will be collected at the research center. The blood sample is immediately placed in a K3 EDTA type tube.

The tube label must be marked with the patient's unique number in the study. Along with the blood sample preparation, a sample form (paper) must be filled out, accompanying the sample during transportation to the laboratory. The sample form must include:

- The patient's unique number or code in the current study;
- The sample tube number (or the tube barcode must be marked).
- Sample volume;
- Purpose of the sample, name of the test.
- Place of sample collection;
- Time of sample collection;
- Time of sample shipment;
- Method of transportation;

The sample should be transported to the laboratory in a special blood sample transport container that ensures compliance with the transportation temperature (from -20° to -80°) regime.

Upon receipt in the laboratory, the sample with the accompanying form will be stored in a storage space (refrigerator) with a temperature regime from -20° to -80°, accessible to authorized study personnel.

The obtained sample will be subjected to analysis for CYP2C19 \*2, \*3 allele genotyping using the RT-PCR-based allele discrimination method. The analytical procedures include the stages of DNA extraction from the obtained blood sample, pre-PCR and PCR, which are performed using DNA extraction reagents and appropriate primers. Appendix 2 presents the main procedural descriptions of the analytical phase of CYP2C19 \*2, \*3 allele genotyping that should be applied in the study.

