## 2.6.2 Determining the Study Sample Size

The study sample size was determined at 240 patients.

In order to achieve representativeness of the sample, strength of evidence, high level of reliability and cost-effectiveness of the study, the minimum sample size calculations were performed using two tools that provided two approximate sample sizes. It is assumed that for the subsequent statistical analysis of the study results for calculating the odds ratio, relative risks and benefits, a larger number of variables would be better, and if the average of these two sizes of the study sample deviates towards the larger one, it was taken as the sample size.

The calculations were performed using the following tools:

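### Simple 1:2 randomisation, with no blocking or centre stratification described, gives 80/160 only on average and guarantees neither 160 genotyped participants nor balance within centres

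*Combined protocol and SAP*

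**What the plan says.** Section 2.6.2 sets the total: "The study sample size was determined at 240 patients". Section 2.3.2 sets the ratio: "study participants will be randomized to the study or control arm by control-to-experiment allocation rate 1:2". It also sets the setting: "Study participants will be recruited from 4 or more clinical centers".

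The allocation method appears in the description of the comparator arm, in the Synopsis (Study arms) and in Section 2.4.2. Controls are allocated "without CYP2C19 genotyping through simple randomization".

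The control arm is given as 80, with no qualifier; among the three arms, only the loss-of-function arm is marked as approximate. Section 2.5.9 says genotyping "should be performed on at least 160 patients randomized to the study treatment arm".

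No section mentions blocks, strata, minimisation or a centre term, either in the allocation or in the statistical methods of Section 2.6.3. Section 7.2 lists a randomisation plan among the sponsor's records, but its content is not in the document.

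**The concern.** The floor of 160 genotyped equals the expected size of the guided group at 240 participants, so there is no margin. Simple randomisation fixes the probability of assignment, not the counts. The same applies inside each centre.

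The centre question matters more than the totals. The plan treats place of care and delivery of care as influences on outcome (Section 2.6.1), and it relies on random allocation to avoid bias (Section 2.5.7). The randomised contrast is the guided group, both genotype arms together, against the ungenotyped control. If the allocation ratio drifts between centres by chance, some of the difference between centres adds noise to that contrast. The analysis section describes no centre adjustment to remove it.

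**Working it through.** **Inputs from the plan.** N = 240; allocation 1:2; simple randomisation; 80 controls; at least 160 genotyped; four or more centres; event rates up to 0.4 (experimental) and 0.6 (control), two-sided alpha 0.05, power 0.8. **Assumptions.** Enrolment stops at 240. Centre sizes are not given and are taken as equal unless stated.

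**1. The plan's split.** 240 × 1/3 = 80 and 240 × 2/3 = 160. The stated counts are reproduced as expected values.

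**2. Spread of the totals.** The guided count is Binomial(240, 2/3).
- SD = √(240 × 2/3 × 1/3) = √53.33 = 7.30.
- 95% range: 146 to 174 guided, so 66 to 94 controls.
- P(fewer than 160 guided) = 0.470.
- P(exactly 160/80) = 0.055.
- P(within 10 of 160) = 0.85.

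**3. Spread within centres.** With four centres of 60, controls are Binomial(60, 1/3): mean 20, SD √(60 × 2/9) = 3.65, 95% range 13 to 27. The chance that at least one centre is 10 or more percentage points away from the 2/3 ratio depends on the number of equal centres:

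| Centres | Size | 95% range, guided | P(at least one centre off by ≥10 points) |
|---|---|---|---|
| 4 | 60 | 33–47 | 0.43 |
| 6 | 40 | 21–32 | 0.70 |
| 8 | 30 | 15–25 | 0.96 |

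**4. Effect on power.** With the plan's rates and n controls, k guided per control, power = Φ{[0.2√n − 1.96√((1 + 1/k)p̄(1 − p̄))] / √(0.24 + 0.24/k)}, where p̄ = (0.6 + 0.4k)/(1 + k). At n = 80, k = 2: p̄ = 0.467, so (1.789 − 1.198)/0.6 = 0.985 and power is 0.838. The same normal approximation asks for 73 + 146 = 219 participants at 80% power, close to the plan's 221.

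| Guided/control | Power |
|---|---|
| 145/95 | 0.863 |
| 150/90 | 0.856 |
| 160/80 | 0.838 |
| 170/70 | 0.811 |
| 175/65 | 0.793 |

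**5. Effect of the remedy.** Simulation of 1:2 permuted blocks of random size 3, 6 or 9, stratified by centre, N = 240, equal centres:
- Four centres: SD of the guided total about 1.0; 95% range 158–162; P(fewer than 160) about 0.28.
- Eight centres: SD about 1.4; 95% range 157–163; P(fewer than 160) about 0.34.
- Controls in a centre of 60: 19 to 21, instead of 13 to 27.

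Unfinished final blocks in each centre cause the remaining shortfall.

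**The case against.** The strongest reply is that simple randomisation is a valid method and the counts are planning figures. They sit under a heading about expected numbers, and both sample-size tools report minima (251 and 221). The 160 in Section 2.5.9 describes laboratory work and is not tied to a maximum N. Enrolling 254 would give a 90% chance, and 259 a 95% chance, of at least 160 genotyped with no change of method. All of this stands, and it is why the counts should be labelled as expected. The replacement rule in Section 2.5.6 is a weaker answer: it places the newcomer in the corresponding group, so the assignment is not clearly random.

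A reader might draw three stronger conclusions that the documents do not support.
- *The method cannot deliver 80/160 or 160 genotyped.* It delivers 80/160 on average and reaches 160 with probability 0.53. The 47% shortfall belongs to the floor alone; the exact split is missed about 95% of the time.
- *The comparison is biased.* Chance differences in arm size or centre mix under valid randomisation do not bias it.
- *The plan declares the randomisation unstratified.* That is inferred from silence, and the randomisation plan listed in Section 7.2 cannot be checked.

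The plan gives no figure for differences between centres, and it uses common eligibility criteria to make cases alike. The gain from centre balance therefore cannot be quantified from the document.

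**Conclusion.** The point holds as a low-severity design improvement. The named method does not secure the stated counts (control range 66 to 94; 0.47 chance of fewer than 160 genotyped at N = 240), and it leaves the ratio within centres to chance (13 to 27 controls in a centre of 60). The cost to power is small: about 0.79 to 0.86 across the likely splits, conditional on the plan's rates of 0.6 and 0.4. What remains is avoidable centre imbalance with no described adjustment.

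The figures for the totals rest on enrolment stopping at 240. The within-centre figures rest on assumed equal centres. The whole point rests on there being no blocking or stratification in the unseen randomisation plan.

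**What to change.** - **Synopsis (Study arms) and Section 2.4.2:** replace simple randomisation with 1:2 permuted blocks stratified by centre, random block sizes (for example 3, 6 and 9), and the list held and concealed centrally. If the existing randomisation plan already does this, say so in the protocol.
- **Sections 2.4.2 and 2.5.9:** restate 80 and 160 as expected counts, because stratified blocks still miss 160 in about 28% to 34% of trials of 240. If 160 is a true minimum, state that enrolment continues until it is reached. A single central list in blocks of 3, 6 or 12 would give exactly 80/160 at 240, but it leaves centres unbalanced (34 to 46 guided in a centre of 60).
- **Section 2.6.3:** name centre as a stratum in a supportive analysis, or where event counts allow. The primary endpoints are deaths. Section 3.2.1 puts its broad set of major cardiovascular and cerebrovascular events at 1% to 10%, or 2.4 to 24 of 240 participants, and cardiovascular death is only one component. Spread over four or more centres, many strata could carry no information.

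**Cost.** A new list before enrolment and a few lines of text. The downside is that the last allocations in a block become slightly more predictable, since arms are disclosed after randomisation and genotyping (Section 2.5.4). Random block sizes and central concealment limit this.
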